3.5 Outcome Measures

Outcome measures will be extracted from the participant's rehabilitation centre file by the associated research investigator for this study at timepoints T1, T2, T3, T4 and are listed here below:

3.5.1 Primary Outcome Measures

Feasibility of delivering the intervention will be in assessed using measures of adherence, acceptability, cost and safety. This will be collected by an allied health clinician at timepoints (T2), (T3) and (T4).

Adherence

Adherence will be measured by each participant in a workbook. The two measures of adherence will be percentage of sessions attended and number of repetitions completed per session will recorded in the participant's rehabilitation centre files. Attaining a personal best is encouraged in each session.

Acceptability

Acceptability will be determined via two methods, extracting perceived exertion (via the Borg Rating of Perceived Exertion (RPE scale)) from the practice sheets of participants at the study site at timepoints (T2), (T3) and (T4) and via purpose-built paper survey post intervention at timepoints (T3) and (T4) (28). The practice sheets will be stored on the participant's rehabilitation centre files. The paper survey will be provided in person by an allied health clinician from the study site. A paper survey was selected as in previous research at the study site there was a poor response to an electronic survey with participants requesting a paper-based survey. We expect the survey to take approximately 10 minutes to complete, participants will be given support to complete the study in clinic or may take the survey home to complete in time allocated outside the intervention. The

participant may receive support from a family member or carer. If requested, the allied health clinician may allocate time to assist in completion of the survey. Using a Likert scale, the survey will ask four questions:

- i) Were you satisfied with the program?
- ii) How easy was it to participate in the program?
- iii) Did the program give you adequate support?
- iv) Would you recommend the program?

They will also be given free text to input an answer to the following questions:

- i) What did you like or dislike about the multidisciplinary aspect of the program?
- ii) What did you like or dislike about the inclusion of Take Charge and participant workbook in the program?
- iii) What did you like or dislike about the amount of practice that was required?

Cost

Cost will be reported by calculating the cost of the program per individual participant based on standard clinic fees. Participants will be charged for the therapeutic program as per usual care at the study site. Participants will not be charged for any research activities include assessments, surveys or research related follow up.

Safety

Safety will be monitored during training sessions by a member of the rehabilitation team and participants will be asked to log any events occurring at home in their participant workbook. All incidents will be recorded in the rehabilitation centre files and reported by the research team.

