3.2 Study Design

The study will look at the feasibility of providing this type of training offered to clients attending the program at the study sites. As part of the intensive program, participants will undertake 45 hours (three hours for five consecutive days over three weeks) of intensive, multidisciplinary practice both in the clinic and at home. At-home therapy will be delivered by video-guided exercise programs or individualised exercise programs. The primary outcome measure for this study will be feasibility, measured by adherence, acceptability, cost and safety. The secondary outcome measures for this study will be mobility, quality of life, self-efficacy skills and goal attainment. Outcome measures will be collected just prior commencement (week 0) (T1), midpoint (second week) (T2), upon completion of the intensive program (third week) (T3) and three weeks post intensive program (T4).

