3.4 Flow of Study

An allied health clinician from the study site will collect demographic information such as age, gender, side of hemiparesis and time post stroke by asking the participant in an initial assessment and using the study demographic form (T1). In the same assessment (T1), the abilities of the participant using the Motor Assessment Scale for Stroke (MAS), Short Physical Performance Battery (SPPB), 2 Minute Walk Test (2MWT), Exercise Self Efficacy Scale (ESES) and the 12-Item Short Form Survey (SF-12) will be taken and recorded in the participant rehabilitation centre files (22-26). The clinician with the participant will then identify an 'area of difficulty' based on an individual activity limitation or participation. The clinician with the participant will establish one primary physical goal for the intervention and up to two secondary goals and score them based on the Goal Attainment Scale (GAS) (27). These outcomes and goals will be recorded the participant's rehabilitation centre files, handed over to treating therapists for the program and recorded in the participant's paper workbook.

Participants will then undergo the intervention and clinicians will record in their practice sheets the exercises completed and participant's perceived rating of exertion for each exercise for the duration

of the intensive program (via the Borg Rating of Perceived Exertion (RPE scale)) (28). After two weeks of the intensive program (T2), a summary of performance outcomes (SPPB and 2MWT) will be taken as an indicator of progress by an allied health clinician (23,24). These two outcome measures will be recorded in the participant's rehabilitation centre files and in a participant's paper workbook.

After the three-week intervention period (T3), an allied health clinician blinded to the preintervention outcome measures of the program will reassess the initial assessment measures (MAS,
SPPB, 2MWT and SF-12, ESES) and rescore the goals (using the GAS) (22-27). These outcomes, along
with the Borg perceived exertion ratings will be recorded in the participant's rehabilitation centre
files (28). Participants will also be given a post intervention survey by the allied health clinician to
determine the intervention's feasibility and effect on self-management and quality of life (this
survey is detailed below). This survey will be completed in allocated time outside the intervention

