6.2 Data Analysis

De-identified data analysis will be conducted using SPSS Version 25. Demographic data will be

reported via descriptive statistics. Adherence data will be calculated from each week and from week 0 (T1) to week 3 (T2) and will be reported as mean repetitions per hour, session, and week and then as a percentage of overall sessions attended. Acceptability and self-management data will be taken from the surveys and will be reported as frequencies comparing time points week 3 (T3) and week 6 (T4). Acceptability data from the practice sheets use will be calculated from each week and from week 0 (T1) to week 3 (T3) and will be reported as mean values per week and then as a percentage overall. Paired t-tests will be used to analyse within group change over time for the clinical outcomes between week 0 (T1) to week 3 (T3) and between week 0 (T1) to week 6 (T4). Differences will be reported as a mean and 95% confidence interval.

7 Research Outcomes and Future Plans

Participants will have the opportunity to review their initial (T1) and post intervention (T3, T4) results with their treating allied health clinician (as per usual care at the study site). A publication and conference presentation are expected from this project to satisfy the requirement of the Master by Research candidature. Participants who have consented to participation in the research will be informed that only de-identified group data will be presented.

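### Both adherence measures, part of the primary outcome, rest on participants' own workbook entries with no described check, even for clinic sessions where a clinician is present

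*Protocol*

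**What the plan says.** Section 3.2 sets the status of the data: "The primary outcome measure for this study will be feasibility, measured by adherence, acceptability, cost and safety". It also places the 45 hours of practice partly in the clinic and partly at home, without giving the split.

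Section 3.5.1, under Adherence, names the instrument: "Adherence will be measured by each participant in a workbook". It then lists the measures and where they are filed: "percentage of sessions attended and number of repetitions completed per session will recorded in the participant's rehabilitation centre files". It does not say who makes that entry. The paragraph closes with "Attaining a personal best is encouraged in each session".

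Section 3.4 describes a second record, kept by staff throughout the programme: "clinicians will record in their practice sheets the exercises completed and participant's perceived rating of exertion for each exercise". Section 6.2 uses that sheet for a different component: "Acceptability data from the practice sheets use will be calculated from each week". Adherence is summarised there as average repetitions by hour, by session and by week, and as a percentage for attendance.

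**The concern.** The person whose adherence is being judged is also the one who measures it. For repetitions, that person is urged each session to beat a previous best, so the count serves both as a training target and as outcome data. In the clinic this is avoidable, because a clinician is there and is already filling in a form.

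What is at stake is how far a reader can trust the adherence result. The hypothesis (section 2.5) predicts that adherence will be high, and research question 1 (section 2.4) lists adherence first among the aspects of feasibility. If the figures come from unchecked self-counts, a favourable result cannot be told apart from generous counting. An unfavourable one cannot be told apart from incomplete workbooks, since a blank page may mean a missed session or an unrecorded one.

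**Working it through.** The protocol gives no figure to reproduce here. The check is to follow the data path and then see what a recording error would do to each reported summary.

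**Data path**

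1. *Origin.* The participant's workbook, for both measures (3.5.1, Adherence).
2. *Filing.* The values go to the centre file; the person entering them is not named (3.5.1).
3. *Collection.* An allied health clinician collects the feasibility data at T2, T3 and T4 (3.5.1, opening), and an investigator extracts outcomes from the centre file (3.5). Both steps move a value. Neither is described as checking it.
4. *Parallel record.* The practice sheet holds exercises completed and exertion for each exercise (3.4). Neither repetitions nor attendance is named as a field.
5. *Use of the parallel record.* Exertion only, under acceptability (3.5.1 and 6.2).
6. *Precedent in the same protocol.* For safety, 3.5.1 has a team member monitor training sessions and uses the workbook for events at home. Adherence has no such split.

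**Sensitivity of attendance**

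Inputs: 5 days a week for 3 weeks (3.2). Assumption: one session per programme day, because the protocol does not define a session.

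- Sessions per participant: 5 × 3 = 15.
- Effect of one wrong entry: 1/15 = 6.7 percentage points.
- With an assumed true attendance of 12/15 = 80.0%: one session over-recorded gives 13/15 = 86.7%, and two give 14/15 = 93.3%.
- In the other direction, one forgotten gives 11/15 = 73.3%, and two give 10/15 = 66.7%.

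**Sensitivity of repetitions**

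Let *f* be the proportional over-count and *m* the number of a week's 5 sessions left unrecorded, with equal true repetitions in each session.

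- Recorded mean per recorded session ÷ true mean = 1 + *f*.
- Recorded weekly total ÷ true weekly total = (1 + *f*)(5 − *m*)/5.

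The protocol gives no value for *f*. Purely as an assumed range, take *f* from 10% to 30%.

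| | *m* = 0 | *m* = 1 |
|---|---|---|
| Per recorded session, *f* = 10% | 1.10 | 1.10 |
| Weekly total, *f* = 10% | 1.10 | 1.10 × 0.8 = 0.88 |
| Per recorded session, *f* = 30% | 1.30 | 1.30 |
| Weekly total, *f* = 30% | 1.30 | 1.30 × 0.8 = 1.04 |

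With one session unrecorded, the weekly total ranges from 12% too low to 4% too high, while the per-session mean is 10% to 30% too high. The two summaries can err in opposite directions, so the net direction is not known in advance.

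**The case against.** Five points can fairly be made against this.

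- **The analysed source is the centre file, and a clinician collects the data.** This is true of the path, but filing and collecting a self-count do not verify it. If clinicians were meant to do the counting, 3.5.1 says otherwise and needs correcting in any case.
- **No better record has been passed over.** This stands. A reader might infer from 3.4 that clinicians already hold the same counts. The documents do not support that, because the sheet is said to contain exercises completed and exertion. What has been passed over is an opportunity, not an existing dataset.
- **The push towards a personal best says nothing about attendance.** This stands. It bears on repetitions only. Over-recorded attendance is also less plausible in staffed clinic sessions, and blank pages would tend to lower the percentage.
- **Self-recording belongs to the programme.** The approach is self-managed, the workbook is part of it, and home practice has no observer. This justifies the workbook for home sessions and as a therapeutic tool. It does not justify making it the only stated source for supervised sessions.
- **Detail may be in the intervention manual.** It may, since section 4.1 refers to a manual that was not available for this review. Section 3.5.1 would still name the participant as measurer.

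**Conclusion.** The point holds as a weakness in the data source. Both adherence measures are stated to be self-recorded, no check is described, and for clinic sessions an observer with a form is already present.

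A reader might go further and infer that the primary adherence result is biased upwards. The documents do not support that. Inflation of repetition counts is plausible given the encouragement, but omissions act the other way on weekly totals and attendance, and neither can be sized from the protocol. Nor should one infer that a false upward trend across weeks would mislead the analysis, because section 6.2 plans descriptive summaries and no trend analysis.

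The consequence is limited. The protocol sets no adherence threshold, so no decision rule is affected. What suffers is the credibility of a descriptive component of the primary outcome in about 15 people, where each wrong attendance entry moves one participant by 6.7 points. That figure assumes one session per programme day, and the repetition figures above rest on assumed over-counts. This is a cheap improvement worth making, not a flaw that invalidates the study.

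**What to change.** - **Section 3.5.1, Adherence:** add attendance and repetitions entries to the clinician's practice sheet, and name that sheet as the source for clinic sessions.
- **Same section:** keep the participant workbook as the source for home sessions, and state that the clinician's record prevails where both exist for a session.
- **Section 3.4:** list the two added entries where the practice sheet is described.
- **Section 6.2:** report clinic adherence (clinician-recorded) and home adherence (self-reported) separately.

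This is the division between clinic and home that the protocol already uses for safety. The programme and the encouragement given to participants are untouched. The cost is some protocol wording, two entries on an existing form and a small added recording task for treating clinicians. Home practice stays self-reported, which separate reporting makes visible. That matters more if practice moves to remote delivery, as section 7.1 allows.

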either at home or in the clinic and if needed an allied health clinician or carer will be available to
support filling out the survey and collecting the surveys from participant. Completed surveys will be
filed in the participant's rehabilitation centre file and in a participant's paper workbook. Participants
will be followed up in three weeks (T4) by the same allied health clinician, who will complete a
follow up assessment to obtain follow up outcome measures (MAS, SPPB, 2MWT, ESES SF-12) and
participants will be asked to complete the same survey again under the same conditions and
provisional support as the first survey (22-26). The results from the survey and the outcome
measures will be filed in the participant's rehabilitation centre file.

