6.1 Data Collection and Management

Data collected at each time point (T1) - (T4) will be extracted from participants rehabilitation centre files with names replaced by individual participants study identification number to organise and collect the data. This data will be stored, in a locked filing cabinet at the study site in paper form.

After the intervention the consenting participants' paper data will be collected by the associate research investigator and converted to electronic files. These electronic files will be uploaded to Excel in a password protected file for storing and analysis. The database housing this information will be stored on a secure Macquarie University server and Cloudstor and will be password protected. Only the named research team will have access to the files. Any paper data will be de-identified and stored in a secured archive onsite at Macquarie University for a period of 7 years post study completion. The electronic data files will be kept on the secure Macquarie University server and Cloudstor indefinitely.

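### Acceptability survey forms, part of the primary outcome, go into the participant's own file at the centre that delivers the programme, which may tilt answers towards approval by an unknown amount

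*Protocol*

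**What the plan says.** Section 3.2 makes acceptability part of the main result: "The primary outcome measure for this study will be feasibility, measured by adherence, acceptability, cost and safety". Section 3.5.1 measures it in two ways: Borg exertion ratings from the practice sheets, and a purpose-built paper survey at T3 and T4. The survey has four Likert items (satisfaction, ease of taking part, adequacy of support, willingness to recommend) and three free-text items on likes and dislikes.

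The route of the survey is fixed as follows.

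- **Hand-out (3.5.1):** "The paper survey will be provided in person by an allied health clinician from the study site".
- **Help (3.5.1):** "If requested, the allied health clinician may allocate time to assist in completion of the survey". The same section says the "participant may receive support from a family member or carer", and that participants "may take the survey home to complete in time allocated outside the intervention".
- **Collection (3.4):** if needed, a clinician or a carer is available to "support filling out the survey and collecting the surveys from participant".
- **Filing (3.4):** completed T3 surveys are "filed in the participant's rehabilitation centre file and in a participant's paper workbook". For T4, survey results go to the centre file; the workbook is not mentioned.
- **De-identification (6.1):** data "will be extracted from participants rehabilitation centre files with names replaced by individual participants study identification number". Section 5.6 has participants told at consent that their survey responses will be taken from their client files and then de-identified.

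The centre developed the programme (4.1) and charges its usual fees for it (3.5.1, Cost). Participants pay for their own attendance (4.2).

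**The concern.** Participants are asked to judge a service, and the form is then kept by the provider of that service in a file that identifies them. Section 5.6 speaks of their ongoing therapy at the centre, so some will expect to keep dealing with the people who hold that file. People who know that a provider can read their rating tend to be kinder than they otherwise would be.

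The likely direction matters. Section 2.5 hypothesises high acceptability, so an error towards approval would support the study's own expectation and not merely add noise. The other acceptability measure, Borg exertion, records how hard the work felt. It does not say whether participants approved of the programme, so it cannot correct the survey.

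This is a data-collection procedure that the protocol itself fixes. It is not something normally left to an analysis plan, and analysis cannot repair it afterwards.

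**Working it through.** The protocol states no figure for acceptability to reproduce: no threshold, no precision target and no expected proportion. The check therefore sets the provisions side by side, with one piece of arithmetic for scale.

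**1. Is the survey part of the primary outcome?** Yes (3.2 and 3.5.1).

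**2. Can the centre link answers to a person?** Yes, by inference. The T3 form goes into the individual's centre file and workbook, and the T4 survey results go into the centre file (3.4). Names are replaced only when data leave that file (6.1). Section 5.6 agrees, since it describes extraction from client files followed by de-identification.

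**3. Will participants know this?** They are told at consent that the responses are taken from their client files (5.6).

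**4. Does any provision stop centre staff from reading the answers?** None is stated. The protocol describes no sealed return, no independent collector and no limit on access within the clinic. The assurances in 5.6 and 5.7 protect the decision to join or withdraw, not candour in the answers. The blinding at T3 and T4 (3.4, 3.5.2) concerns earlier outcome measures.

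**5. Could the design expose the bias?** No. There is one group (3.1), so there is no comparator. Section 3.4 repeats the survey at T4 under the same conditions and with the same clinician. The planned comparison of T3 and T4 frequencies (6.2) would carry the same tilt on both sides.

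**6. Scale.** Section 5.5 gives about 15 participants. If all respond, one answer that moves from not approving to approving changes a reported frequency by

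1 / 15 = 0.067, or 6.7 percentage points.

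Two such answers change it by 2 / 15 = 13.3 points, and three by 3 / 15 = 20.0 points. These figures show how sensitive the result is to each answer. They do not estimate how many answers would shift, on which the protocol gives no information.

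**The case against.** The best case for the plan is that much of the pressure has already been taken out of completion. The form can be filled in at home, and a relative or carer may help. Clinician help is given only on request or if needed, and a carer may be the one who helps with collection. The free-text items ask about dislikes as well as likes, which invites criticism. In-person paper delivery has a stated reason: an earlier electronic survey at the site had a poor response. The study is a descriptive feasibility study with no acceptability threshold, so no stated decision turns on a few points either way.

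All of that stands, and it rules out several stronger readings that a reader might infer:

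- **That participants answer in front of their own therapist.** The protocol does not say so. Section 3.4 has the T3 clinician blinded to the pre-intervention measures, while T1 outcomes and goals are handed over to the treating therapists. The person giving out the survey is therefore probably not one of them, although still a member of site staff.
- **That clinic staff always collect the form.** Help with collection is conditional, and a carer may give it.
- **That the form itself carries a name.** No section says this. What is identifiable is the file in which the form is kept.
- **That therapists use the workbook containing the survey.** The workbook is described as the participant's, and therapists' use of it is not stated.

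What the objection does not reach is the filing. A form completed in private at home still ends up in the client's file, and this applies to every participant.

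**Conclusion.** The point holds as a foreseeable risk, not a demonstrated bias. Identifiable ratings of a self-funded programme are stored where the centre that delivers it can read them. This may move answers towards approval, the direction of the study's hypothesis, and nothing in the design would show it.

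The amount is unknown. A reader might be tempted to convert the risk into a definite shift in the proportion satisfied, but the protocol offers no baseline proportion and no basis for a number of shifted answers. The supportable statement is 6.7 points per shifted answer, assuming about 15 respondents.

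The conclusion rests on two assumptions: that centre staff can open the centre files, and that participants, having been told where their responses are held, may answer with that in mind. The existing safeguards reduce pressure while the form is being completed but not the effect of filing. This is a cheap improvement to one component of the primary outcome, not a flaw that undermines the study.

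**What to change.** Keep the paper survey and the in-person hand-out, and change what happens to the form in sections 3.4, 3.5.1, 5.6 and 6.1:

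- Label the form with the study number only, before it is given out.
- Supply an envelope, and have the form returned sealed to the research investigator, who under section 6.1 already collects the paper data.
- Do not file the form or its results in the centre file or the workbook, at T3 or T4.
- Tell participants, at consent and on the form, that clinic staff will not see individual answers.
- Where help is needed, prefer a family member or carer. Keep clinician help as the fallback.
- Record on the form whether help was given and by whom, so that assisted answers can be described separately.

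The cost is envelopes and a few lines of wording. Possibly a few forms will be late or missing, which also matters with about 15 people, and the clinic will not see individual comments during the study.
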